Preliminary Studies. The PI ([name]) developed the Family Intervention: Telephone Tracking intervention (R21MH062561; [6]) and demonstrated efficacy of the intervention (R01NR010559; [10]), showing that compared to a supportive intervention, the FITT-C reduced caregiver depressive symptoms and their reactions to patient memory and behavior problems. A recent secondary analysis showed that the FITT-C reduced ER visits and hospital stays among caregivers and increased the use of community resources compared to a supportive intervention (11). We have a detailed treatment manual that includes sample dialogue, intervention strategies, and strategies for management common behavioral problems in dementia that will available for use in the current study. The PI and other members of our research group also developed a mind-body intervention that we tested in a randomized clinical trial in 122 individuals with depressive symptoms who were taking antidepressant medications (R01NR012005; [12]). Results showed that the 10-week intervention reduced depressive symptoms at 6-month follow-up compared to a healthy living educational program. As part of developing this project, we started a collaboration with the computer/biomedical engineering group from the University of Rhode Island (URI; led by [name] serving as a Co-I in this proposal). [name]'s team has developed and deployed a number of mHealth technologies with medical and psychiatric patients including SPARK (25), EchoWear (26-28), Android EAR (29-31), and Face Emotion Monitoring (32,33). **Overall, our multidisciplinary research team is uniquely positioned to conduct this study.**

Aim 1 Approach. We will work closely with computer engineering scientists at URI to translate the caregiver and mind-body interventions into a mobile App. We will then beta test the App in 10 dementia caregivers for one month. Specific recommendations from these caregivers will be obtained via individual qualitative interviews and questionnaires measuring technical issues and content use. Based on this information, the App will be expanded, modified, and translated to be a more effective and user-friendly tool. The research team will meet weekly

over *nine months* to review progress and provide input about content and functionality of the App. For both interventions, we have detailed treatment manuals that will be used to identify specific content.

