Phase 1. Translation of intervention. In this step (6 months), we will work with Co-I [name] to design the App and add intervention content. In preliminary discussions, we have identified equipment needed for the study and developed a preliminary outline of the App components (see below and Figure 1).

Technical issues. The mHealth App will be designed for the android platform. We chose this platform because of simplicity in implementation and time and financial limitations of the current award. Future projects will allow for development for other platforms including iOS (iPad or iPhone). In addition, we chose to provide all participants in the study with android tablets to standardize operating procedures and minimize troubleshooting of multiple personal devices. We will restrict participants' access within the tablet to the CARE-Well, Gmail, and Zoom Apps only. Future projects will incorporate personal devices to increase accessibility and applicability of the intervention. All App data will be stored on participants' tablet devices but will not include any personal or health information. At completion of each study phase, data will be downloaded into a password-protected database for analysis. The message forum (described below) will involve a Google group that is embedded in the App. [name]'s team at URI will provide technical support for participants and will develop troubleshooting procedures but will not have access to personal or health information. Our partner will also develop an orientation training and video about how to use the App.

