Phase 2. Beta Testing and Modification of the CARE-Well App. In this step (3 months), we will recruit 10 dementia caregivers to use the App for one month and then elicit feedback to modify and adapt the intervention. We will use purposive sampling to select diverse caregivers across sex, relationship type (spouse, adult child, other), race/ethnicity, and severity of dementia in care recipient. Otherwise, recruitment will be based on inclusion/exclusion criteria outlined in Aim 2. Participants will be recruited from multiple sources, including the Rhode Island Hospital (RIH) Alzheimer's and Memory Disorders Center (two full-time neurologists seeing only aging and dementia cases; 728 new cases and 1,352 follow-ups annually), RIH Neuropsychology Program (6 full-time adult clinicians seeing about 50% older adult referrals; approximately 200 new dementia cases annually), and community advertising (including the Alzheimer's Association, RI Chapter). Our research team has used these strategies previously to recruit almost 300 dementia caregivers for two intervention studies. Participants will be delivered a package that includes: one android tablet; two copies of the consent form and one prepaid postage envelope to return the signed consent form (if electronic consent form is for some reason inaccessible or unable to be completed for other reasons). A member of the study team will review the consent form (whether paper or electronic) with participants during a Zoom video call on the tablet. They will be instructed to sign and initial the form and send it back to the study team either via REDCap or in the prepaid postage envelope so that a member of the study team can sign it and send a signed copy back to them. Participants will be instructed to keep the unsigned copy in their records as a reference. Once a participant completes the consent process during the initial Zoom call, they will be given a de-identified Gmail username and password for the computer tablet/ App and will be shown how to operate the device and use the App. After one month of use, they will complete and participate in in-depth, semi-structured interviews with two interviewers (clinical researcher and computer engineer). Interviewers will assure participants of privacy and emphasize confidentiality. Interviews will last approximately 30 minutes. Each interview will take place in a private location, will be digitally recorded with audio and video (via Zoom), and transcribed using NVivo software (QSR International, 2018). The interviews will follow a standard discussion guide, include probes to explore and seek clarification, and will address the participants' experience with technical aspects of the App and content (see appendix for sample questions). We will also have quantitative data about frequency of App and component use. The PI along with [name] will conduct the qualitative data analysis by identifying themes that can help with modifications

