
of the user interface and content. We plan one month for modifications prior to beginning the feasibility study.

Aim 2 Approach. In this aim, we will conduct a feasibility trial, in which 40 dementia caregivers will be randomized to receive a computer tablet preloaded with the CARE-well App or preloaded with internet links relevant to dementia and caregiving. Electronic outcome measures (detailed below) administered via REDCap secure web platform will be assessed at baseline and end of intervention (3 months) during each study visit. To measure sustainability of the App, the first 10 caregivers from each group will be offered the tablets for an additional month to monitor usage of the App outside the formal trial. The goal of this aim is to determine feasibility of the intervention, study procedures, and outcome measures.

Participants & Recruitment. Informal caregivers of individuals (aged 18 and older) who are formally diagnosed with mild-moderate Alzheimer's disease or related dementia (e.g., Lewy body dementia, frontotemporal dementia) documented by a neurologist, psychiatrist, or geriatrician will be screened for study eligibility (diagnoses will be confirmed via a release of information signed by the care recipient). Care recipients must be living in the community, not in nursing homes or assisted living facilities. Care recipients cannot have another serious, active medical illness besides dementia. Caregivers will be recruited from the RIH Alzheimer's and Memory Disorders Center and RIH Neuropsychology Program by communication between the patients' clinicians and their caregivers. In this way, we will obtain consent to contact the caregiver. In addition, we will provide letters to clinic patients that will invite their caregivers to participate in the study. Community advertising will also be implemented. We will recruit for 11 months (Month 11-Month 21) and will need to recruit about 3-4 caregivers per month. **In the past FITT-C trial, we had a recruitment rate of 4.7 caregivers per month.**

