Inclusion/Exclusion Criteria. Inclusion criteria include: 1). adequate English-speaking and reading skills; 2). provide at least 4 hours of supervision per day for the care recipient (either directly or by telephone); 3). live in the community (either with the care recipient or without); 4). have provided supervision/assistance for at least six months prior to enrollment and have no plans for to place the care recipient in long term care or to end their role as caregiver within six months of study enrollment; 5). report some degree of distress associated with caregiving, which will be assessed through endorsement of two of nine negative experiences associated with caregiving (feeling overwhelmed or stressed, sad mood/depression, anger/frustration, loss of contact with family and friends, conflict in family or family stress, neglecting own health, demands or pressures from caregiving, exhaustion/fatigue, not taking care of their own needs or other responsibilities); and 6) access to WIFI at home. Exclusion criteria include: 1). major acute medical illness; 2). severe mental illness (e.g., bipolar, schizophrenia); or 3). diagnosed cognitive impairment.

Procedure & Interventions. After screening and consenting, caregivers will complete an electronic baseline assessment (described below) and will be randomly assigned to receive a computer tablet that has the newly developed CARE-Well App or internet links relevant to dementia caregiving for 3 months. We will provide the caregivers with written information about expectations for the App use at orientation and they will be encouraged to use the website links daily. Computer engineers and/or a research assistant will provide IT support for caregivers in both groups. To minimize face-to-face contact during the COVID-19 pandemic, caregivers will remain at home to complete the second and final study 'visit,' which entails completing follow-up assessments within two weeks of intervention completion. Once follow-up assessments are complete, participants will be instructed to send the computer tablet back to RIH using a prepaid package given to them during their initial study visit. Due to time limitations of the current award, the first 10 caregivers in each group will be offered to keep the tablets and continue to use the App or internet links for an additional month to estimate intervention sustainability.

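### The tablet restriction does not fit the control arm, and the once-a-day adherence benchmark does not match the frequency of use that participants are asked to meet

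*Protocol*

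**What the plan says.** **Tablet content.** Technical issues (Aim 1, Phase 1) explains that "we chose to provide all participants in the study with android tablets to standardize operating procedures", and then limits participants' "access within the tablet to the CARE-Well, Gmail, and Zoom Apps only". It names no arm and no exception. Aim 2 Approach has 40 caregivers "randomized to receive a computer tablet preloaded with the CARE-well App or preloaded with internet links relevant to dementia and caregiving". Procedure & Interventions repeats that split.

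**Frequency of use.** Four places state it:

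| Section | Applies to | Frequency |
|---|---|---|
| Intervention Description | App | four or more times a week |
| Procedure & Interventions | links | daily: "they will be encouraged to use the website links daily" |
| Study Procedures, Materials, and Potential Risks (Aim 2 text) | App or links | four or more times a week |
| Outcomes and Analyses | App or links, as the scoring rule | once a day or more |

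**Usage data.** Technical issues says that App data are stored on the tablet, and that "At completion of each study phase, data will be downloaded into a password-protected database for analysis". For the beta test, Aim 1 Approach mentions "questionnaires measuring technical issues and content use", and Phase 2 adds: "We will also have quantitative data about frequency of App and component use". For the additional month offered to the first 10 caregivers in each group, Aim 2 Approach gives the purpose as "to monitor usage of the App outside the formal trial", whereas Procedure & Interventions has participants continuing with the App or the links. The App use paragraph under Potential Problems and Alternative Strategies plans more reminders if use of the App or the links is low.

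**The concern.** The restriction is the only description of how the tablets are configured, and it does not describe a control tablet. Anyone who configured tablets from that paragraph would allow on control devices the App that defines the other arm, and would find no instruction for giving access to the links.

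The adherence benchmark is one of the stated outputs for planning a full trial. If participants are asked for one frequency and scored against a higher one, the percentage mixes true non-adherence with compliance with the request. A low figure could then be read as a weak App or a weak control condition when it partly reflects the scoring rule.

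Link use matters for the same reason. The benchmark covers both arms, so the control arm needs a day-by-day record of use, and the protocol does not say what that record is.

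**Working it through.** The protocol gives no figure of its own to reproduce. The check is a comparison of sections, with a little arithmetic on frequency.

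**1. Does the restriction reach the control arm?** The paragraph sits under Aim 1, where there is no control arm, but its wording is study-wide: tablets go to all participants, and data are downloaded after each study phase. The permitted list has three items: CARE-Well, Gmail and Zoom. The control condition is a set of links in place of CARE-Well. So one permitted item (CARE-Well) does not belong on a control tablet, and the one thing that does belong there (the links) is not on the list.

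**2. Can a participant do what is asked and still be scored non-adherent?** Inputs: a minimum of 4 uses a week (Intervention Description; Study Procedures, Materials, and Potential Risks), a scoring rule of at least one use a day (Outcomes and Analyses), and a 3-month intervention, taken here as 13 weeks, or 91 days.

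- Days with use in a week, at exactly four uses: at most 4, if each falls on a different day. Share of days: 4 / 7 = 57.1%.
- Over 3 months: 4 × 13 = 52 days with use at most, so at least 91 − 52 = 39 days without use.
- Benchmark read as every day: 7 of 7 days are needed. The participant falls short by at least 3 days a week and is scored non-adherent.
- Benchmark read as an average: 4 / 7 = 0.57 uses a day, which is below 1, so the result is the same.

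This applies to the App arm under both sections that ask for four or more uses a week. It applies to the control arm under Study Procedures, Materials, and Potential Risks. Under Procedure & Interventions, control participants are asked for daily use, which does match the benchmark. Reading only the Intervention Description and Procedure & Interventions, the two arms are therefore asked for different frequencies and scored by one rule.

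**3. Where would control-arm usage come from?** Of the seven benchmarks in Outcomes and Analyses, two depend on usage: adherence, and continuation with frequency of use. Adherence names the links directly. Continuation is worded in terms of the tablet or App but covers 10 caregivers from each group, that is 10 × 2 = 20, of whom 10 are controls continuing with links. The usage data described explicitly are App data. The questionnaires and component counts belong to the beta test, so what reaches the feasibility trial is the download and the additional-month monitoring of the App. The reminder plan assumes that someone can see when link use is low but gives no method.

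**The case against.** **On the restriction.** It was probably written with App tablets in mind, since the paragraph opens with the App's platform and the control arm appears only later. The more specific Aim 2 text, which preloads links for controls, would naturally govern. The restriction also need not block web pages opened from a permitted app; CARE-Well itself links out to community resources. All of this stands. A reader might infer that control participants cannot reach their links, or that controls are meant to have the App. The documents support neither: Aim 2 Approach gives the App to one group and the links to the other. What remains is a paragraph that contradicts that description if followed literally.

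**On frequency.** Daily use satisfies a request for four or more uses a week, so those two instructions do not exclude each other. The benchmark is a descriptive percentage with no pass mark, and the 39-day figure assumes someone who stops at the minimum. These points limit the consequence but leave the mismatch between request and scoring in place.

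**On link use.** A reader might infer that control-arm adherence cannot be measured at all and is lost for good. That would be an argument from silence. The reminder plan shows that link use is meant to be observed, the download sentence says data without limiting it to the App, and device-level tablet use could meet the continuation item as worded. The capture method may also sit in an operations document. The protocol does not say that link use goes unrecorded; it only leaves the source unstated.

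**Conclusion.** Two statements are wrong as written and should be corrected, and one is a secondary clarification.

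- The tablet restriction conflicts with the control condition. It affects every control tablet; the allocation ratio for the 40 caregivers is not stated, so that number is not given here.
- The requested frequency and the adherence benchmark disagree in both arms, not only in the control arm. Use exactly at the four-a-week minimum gives at most 57% of days (52 of 91, with 3 months taken as 13 weeks). It fails the benchmark read as every day, and also read as an average. How many participants would sit at or near that minimum is unknown, so the effect on the reported percentage cannot be estimated.
- The source of link-use data is unstated for the control part of two of the seven benchmarks, including 10 of the 20 caregivers offered the additional month.

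None of this stops a feasibility trial that is not powered for efficacy. It affects how two of its outputs can be read.

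**What to change.** 1. In Technical issues, make the restriction arm-specific: CARE-Well, Gmail and Zoom on App tablets; the links with Gmail and Zoom, and not CARE-Well, on control tablets.
2. Reconcile Intervention Description, Procedure & Interventions, Outcomes and Analyses, and Study Procedures, Materials, and Potential Risks, so that adherence in each arm is scored against the frequency that participants are asked to meet. Which frequency to keep is for the investigators. State also whether the benchmark means every day, an average, or a share of days.
3. Capture dated link use on control tablets prospectively, by any simple means, and name it in Outcomes and Analyses as the source for control-arm adherence. A purpose-built links page that logs openings is one option, not a requirement.
4. In Aim 2 Approach, extend the additional-month monitoring from the App to the App or internet links, in line with Procedure & Interventions.

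Items 2 and 4 need only changes of wording. Item 1 needs one clause and a matching control-tablet configuration. Item 3 needs a sentence and whatever capture method is chosen, in place before control tablets go out. The on-device storage and end-of-phase download can stay as they are.

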Intervention Description. The overall intent of the CARE-Well mobile App is to replicate the content and strategies in the telephone-based FITT-C intervention and to integrate the mindfulness and meditation exercises with FITT-C components (see Table 1). Caregivers will be encouraged to use the App at least four times per week. Caregivers will be prompted to complete an in-App, weekly assessment of key areas (i.e., family functioning, health, mood, social support, and care recipient behavior problems) that will allow for tailoring of intervention components. As caregivers complete recommended components, they will receive rewards within the App. Reminders will be used to increase accountability for tasks assigned and for recommended readings. Embedded in the App will be an online caregiver community (Google group), in which caregivers can anonymously post and respond to messages under a username that is in no way connected to personal Gmail accounts. The research team will recommend against posting any personal or identifying information; however, it is ultimately up to the participant to decide whether or not they want to post more personal information. The Google group will be monitored by the research team who may also provide comments, corrections, and links to helpful material. Allowing caregivers to respond to each other will provide social support and identify content that could be added to the App. Other App components will include:

- *Psychoeducation* – general education about dementia and caregiving; educational components about family functioning, healthy living strategies, managing mood, and seeking social support
- *Community Resources* – listing and links to community supports
- *Daily positive messages* including some that focus on positive aspects of caregiving
- *Managing behavior problems* in care recipient –as part of the FITT-C, we developed a common behavior problem guide that includes recommended strategies to manage behaviors. We will use this guide to develop an interactive problem-solving approach.
- *Stress management exercises* – based on the mind-body intervention video/audio segments of breathing practices, guided meditation/relaxation exercises, simple yoga poses, and mindfulness themes
- *Setting a task directive* – based on caregiver assessments, certain tasks related to social support and family functioning will be recommended.

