Outcomes and Analyses. The primary goal of this project is to demonstrate feasibility of the CARE-Well App and study procedures to support a future trial. As such, the study is not

powered to determine efficacy, but rather to determine 1) whether a future trial will be successfully conducted; and 2) whether an in-person caregiver intervention can be reasonably adapted into a mobile App. We will focus on the following (benchmarks in parentheses):

- Identify the best recruitment sites and methods (% who enrolled from each source and % contacts received from each recruitment method)
- Determine participant willingness to be randomized (% who decline participation because of randomization)
- Establish study enrollment rate and retention (latter variable examined by group)
- Determine adherence to intervention (% of participants who use the App or internet links at least once per day)
- Calculate timing of assessments and completion rates (% of assessments completed within two weeks of study enrollment and intervention completion)
- Determine interest in continuation of tablet/App use (along with frequency of use) after formal trial in a subset of caregivers (10 from each group) as an estimate of sustainability
- Collect ratings of satisfaction with technology and content (% satisfied or very satisfied)

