Future Trial: Any challenges, recommendations from participants, and innovative solutions that emerge through the proposed project will assure the CARE-Well App will be well-developed and ready for testing in future trials. The next step will be a fully-powered efficacy study in a large sample of dementia caregivers. We will also examine the effect of CARE-Well on specific outcome measures (including behavioral change outcomes) as described above, examine moderators (mechanisms) of treatment (e.g., App usage, component analysis, caregiver characteristics), and compare the effect sizes of CARE-Well to the FITT-C telephone intervention. In the next stage of the intervention, we will examine sustainability of CARE-Well through monitoring usage and feedback from study participants. Given the widespread availability of mobile technology and internet access, we anticipate efficiently moving from efficacy to dissemination. We hope to disseminate the intervention on a community-level, where specific facilities or agencies can tailor the intervention as needed and post specific content in the message forums. Our future trial will combine Stage II (pure efficacy) and Stage III (community efficacy) components. In particular, we will examine the effect of study/setting (memory clinic, agency, community) on effectiveness and utilization of the App.

Potential Problems and Alternative Strategies

App development time. Although we plan on App development in 6 months, we may encounter issues that slow the process. If so, we will adjust the timeline and engage in early recruitment for both beta testing and the feasibility trial.

Recruitment and attrition. Although our team has extensive experience recruiting dementia caregivers, we may encounter barriers to recruitment. If so, we will use community advertising or other methods. In addition, we will recruit an initial cohort while working on Aim 1, so we have a group ready to use the App as soon as the feasibility trial begins.

App use. If we encounter low App or internet links use, we will increase reminders to participants. Older adults (who will likely comprise 50% of our sample) are increasingly using touchscreen devices (40) and accept and use tablet technology (41), suggesting that this would not be a confounding factor to the proposed App.

Protection of Human Subjects

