All research contained in this proposal will be approved by the Rhode Island Hospital IRB before initiation. Written informed consent will be obtained for all participants.

1. Risks to Human Subjects

a. Human Subjects Involvement, Characteristics, and Design

We will enroll a total of 50 caregivers of persons with dementia. Specific inclusion and exclusion criteria are detailed below. In Aim 1 of the study, 10 participants will participate in a one month use of the CARE-Well application. In Aim 2, 40 participants will be randomly assigned to receive 3 months of either the CARE-Well application or internet links in a feasibility study. They will be enrolled in the study for 3 months. This project will be a collaboration between Rhode Island Hospital and the University of Rhode Island (URI). Investigators at URI will engage in building the application and will participate in qualitative interviews as part of Aim1.

Inclusion/Exclusion Criteria. Inclusion criteria include: 1). adequate English-speaking and reading skills; 2). provide at least one hour of supervision per day for the care recipient (either directly or by telephone); 3). live in the community (either with the care recipient or without); 4). have provided supervision/assistance for at least six months prior to enrollment and have no plans for to place the care recipient in long term care or to end their role as caregiver within six months of study enrollment; 5). report some degree of distress associated with caregiving, which will be assessed through endorsement of two of nine negative experiences associated with caregiving (e.g., feeling overwhelmed, sad mood, frustration, loss of family/friend contact, family conflict, etc.); and 6) access to wifi at home. Exclusion criteria include: 1). major acute medical illness; 2). severe mental illness (e.g., bipolar, schizophrenia; or 3). diagnosed cognitive impairment.

b. Study Procedures, Materials, and Potential Risks

Ten participants will be given an android tablet and asked to use a mobile application at least four times per week for one month. They will then participate in a qualitative interview in which they will be queried about technical and content aspects of the application. Participants in Aim 1 will be compensated \$50.00 in the form of a check

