request at time of completion. As part of Aim 2, 40 participants will be complete baseline assessments and be randomly assigned to the CARE-Well application or internet educational links. They will be encouraged to use the application or links at least four times per week. Data will be collected via paper-pencil assessments from participants at two timepoints (Baseline and End-of-Treatment). The assessment measures will address mood, burden, reactions to behavior problems, health-related quality of life, sexual disinhibition in the care recipient, and desire to institutionalize the care recipient. The data from participants' in-App weekly assessments of key areas will be programmed (using a computer algorithm) to generate personalized recommendations and references to relevant resources within the App. This data will not include any personal or health information and will not be extracted from the App. Participants in Aim 2 will be compensated \$50 at study completion in the form of a check request. Any hard copies of data will be stored in locked file cabinets in a locked office. Electronic data storage will be in a password-protected database.

There are no serious risks associated with participating in this study. Participants will undergo testing with standardized questionnaires and measures. They may feel slightly frustrated, fatigued, or bored when completing these tests. Because we will assess depression, there is a possibility that participants will report severe depression and/or suicidality. In addition, they are providing care for persons with dementia and we may uncover neglect or abuse.

2. Adequacy of Protection Against Risks

Confidentiality will be protected in the following ways: (1) participants' names will not be included on the App, data sheets, or in the computerized database, (2) all data will be kept in a locked file cabinet in a locked office, and (3) the computer database will be password protected and only accessible by the researchers.

a. Informed Consent and Assent

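### Adherence is scored as daily use, but App users are asked for at least four uses a week and the links carry two different frequencies, so caregivers who follow the instruction can be counted non-adherent

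*Protocol*

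**What the plan says.** Four places in the protocol give a frequency of use that bears on Aim 2.

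- **Benchmark, both arms** (Aim 2 Approach, Outcomes and Analyses): "Determine adherence to intervention (% of participants who use the App or internet links at least once per day".
- **App, general description** (Aim 1, Phase 1, Intervention Description): "Caregivers will be encouraged to use the App at least four times per week".
- **Links** (Aim 2, Procedure & Interventions): "they will be encouraged to use the website links daily". The same sentence deals with the App separately and gives no number: "We will provide the caregivers with written information about expectations for the App use at orientation".
- **App and links, Aim 2** (Protection of Human Subjects, 1b): "They will be encouraged to use the application or links at least four times per week".

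Section 1b also gives the four-per-week dose for the one-month Aim 1 test, where participants are "asked to use a mobile application at least four times per week for one month". That is background here, because the benchmark belongs to Aim 2. Under Potential Problems and Alternative Strategies the protocol adds: "If we encounter low App or internet links use, we will increase reminders to participants". It does not say which frequency counts as low.

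**The concern.** An adherence measure should tell the reader whether participants did what they were asked to do. Here the threshold is higher than the minimum asked of App users, so the reported percentage would mix two groups: caregivers who did not follow the instruction, and caregivers who followed it on a less-than-daily schedule. The links arm has a further problem, because the protocol gives it two different instructions.

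Adherence is one of seven feasibility items in a study whose stated primary purpose is to show feasibility for a later trial. A low figure could be read as poor uptake of the App when it partly reflects a threshold that users were never given. If the two arms are in fact told different frequencies, a single daily threshold suits the links arm and not the App arm, and any side-by-side reading of the two percentages is tilted by the instruction alone.

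**Working it through.** The protocol gives no expected adherence figure, so there is nothing to reproduce. The check compares the stated frequencies.

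**Inputs.** The benchmark is at least 1 use per day, or 7 per week (Outcomes and Analyses). The App instruction is at least 4 per week (Intervention Description; Protection of Human Subjects 1b). The links instruction is either daily (Procedure & Interventions) or at least 4 per week (Protection of Human Subjects 1b). Size and duration come from Protection of Human Subjects 1a: "In Aim 2, 40 participants will be randomly assigned to receive 3 months of either the CARE-Well application or internet links in a feasibility study". Two assumptions are needed: 3 months is 12 to 13 weeks, and allocation is 20 per arm.

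**Step 1: instruction against benchmark.** For k uses per week, the average per day is k/7 and the total is k × weeks.

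| Uses per week (k) | Per day (k/7) | Total, 12 weeks | Total, 13 weeks | Meets instruction (at least 4/week) | Meets benchmark (at least 1/day) |
|---|---|---|---|---|---|
| 4 | 0.57 | 48 | 52 | yes | no |
| 5 | 0.71 | 60 | 65 | yes | no |
| 6 | 0.86 | 72 | 78 | yes | no |
| 7, one each day | 1.00 | 84 | 91 | yes | yes |

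The protocol does not say whether once per day means every day or on average. Four to six uses a week fail both readings: they cover at most 4 to 6 days in 7, and their average is below 1.

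**Step 2: which instruction governs.**

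- If the Intervention Description and Procedure & Interventions govern, the App arm is asked for at least four uses a week and the links arm for daily use. The benchmark then matches only the links arm.
- If Protection of Human Subjects 1b governs, both arms are asked for at least four uses a week. The benchmark then matches neither arm.

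Under either reading the App arm's instruction and its benchmark differ. The orientation sheet is not part of the document, so what participants are actually told cannot be settled from it.

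**Step 3: effect on the reported percentage.** Let m be the number of App caregivers who use it 4 to 6 times a week. Scoring them non-adherent lowers the pooled figure by m/40 and the App arm's figure by m/20.

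| m (assumed) | Pooled, points | App arm, points |
|---|---|---|
| 0 | 0 | 0 |
| 1 | 2.5 | 5 |
| 5 | 12.5 | 25 |
| 10 | 25 | 50 |

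The protocol gives no basis for choosing m. The table shows only how quickly the figure moves in a trial of this size.

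**The case against.** Several points can fairly be made for the protocol.

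- **Four a week is a floor.** A daily user satisfies both rules, so instruction and benchmark are not logically incompatible. This is true, but it does not help the caregiver at four to six uses a week.
- **The Human Subjects text may be out of date.** It disagrees with the main Approach elsewhere: paper assessments against REDCap, face-to-face consent against Zoom, one hour of supervision against four. If its dose sentence is set aside, the links have one frequency, daily, which agrees with the benchmark. The App's four-per-week instruction still conflicts with it, and the two arms then have different targets.
- **The links sentence is ambiguous.** Its grammatical subject could be all caregivers rather than the links arm. Reading it as the links arm is an inference, though a natural one, since it concerns the website links and treats the App separately. For the links, the conflict with section 1b remains either way.
- **Unequal instructions are not established.** They arise only if section 1b does not govern. This stands, and that part of the harm is conditional.
- **Different products may have different doses.** This is a legitimate design, but each arm would then need scoring against its own instruction, which the single benchmark does not do.
- **Little hangs on the number.** There is no pass mark and no test, only retention is specified by group, and App use could be re-tabulated at four per week if logs are kept. The step of 2.5 or 5 points is what any reclassified participant would contribute. All of this is correct and limits the seriousness.

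**Conclusion.** The point holds. The benchmark as written does not measure adherence to the use that App participants are asked for, and the protocol states two frequencies for the links. The mismatch is certain from the text. Its numerical effect is not: it depends on how many caregivers settle at four to six uses a week, which may be none. The duration in weeks and equal allocation are assumptions, but the classification result needs neither.

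This should be fixed, but it does not threaten the trial. It affects the meaning of a descriptive feasibility figure, not a formal decision. The part that later analysis could not repair is a difference in what the two arms are told at orientation, if such a difference exists. An analysis plan could redefine the metric but could not change that.

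**What to change.** Before participants are oriented:

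1. Choose one usage instruction, identical in both arms, for example at least four times a week. State it in the Intervention Description, Procedure & Interventions, Protection of Human Subjects 1b and the orientation sheet. If different doses are intended, say so and score each arm against its own.
2. In Outcomes and Analyses, define adherence against that instruction and report it by arm: either the percentage of participants meeting the instructed frequency, or the proportion of weeks in which each participant met it. Say whether the count is of sessions or of days with any use.
3. Keep daily use, or mean days of use per week, as a descriptive summary.
4. Use the same frequency to decide when use is low enough to trigger extra reminders.

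If anyone has already been oriented, record which frequency they were given.

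The cost is wording in four protocol sections and one participant sheet. Frequency of App use is already described as collected in Aim 1. Logging of links use is presupposed by the current benchmark but not described, so it should be confirmed.
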